7 ANALYSIS OF SECONDARY, EXPLORATORY, AND SAFETY OUTCOMES

Final analysis of the secondary, exploratory, and safety outcomes will be implemented separately for each study arm by comparing each active drug group with the corresponding pooled placebo comparator group. The effect of active agent versus placebo on the odds of binary and ordinal outcomes will be quantified using logistic and proportional odds logistic regression. Quantitative outcomes will be analyzed using a linear regression method. In order to preserve consistency across statistical analyses, we will uniformly apply a Bayesian approach using flat priors. Odds ratio, hazard ratio, and differences in mean estimates will be presented with a 95% credible interval.

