analyses, the route and frequency of placebo will be ignored, and all placebo participants will be pooled together as a single group. In comparing an active drug versus placebo, only those placebo participants that were eligible for the active drug will be considered. Randomization will be implemented using permuted blocks, stratified by site and eligibility group. A block size multiplier, either 1 or 2, will be selected uniformly at random for each block. Blocking ensures balance within strata across each active and corresponding pooled placebo group and across study arms at the end of each block. Placebos that match the route (e.g., intravenous vs oral) and frequency of the corresponding active agent further ensure patient and assessor blinding. Which study arm the participant enters will be known to the research sites and the participants, but assignment to active versus placebo will be blinded. The randomized assignment, concealed from the research team, will be transmitted to the site pharmacy who will provide study medication. The participant, treating clinicians, study personnel (other than the investigational pharmacist, medical monitor, and the unblinded statistician who prepares closed session DSMB reports), and outcome assessors will all remain blinded to group assignment until after the database is locked and blinded analysis is completed. The medical monitor will remain blinded except as required for individual patient safety. In cases in which unblinding of the medical monitor is required for individual patient safety, assessment of adverse events by the medical monitor will be performed prior to unblinding. After assessing adverse events, the medical monitor will communicate directly with Coordinating Center to receive the unblinded group assignment needed to inform individual patient safety. The medical monitor will not discuss any unblinded information with blinded trial personnel. If an additional adverse event occurs for a patient for whom the medical monitor has been unblinded for individual patient safety, an alternate medical monitor will be appointed to review the adverse event and determine seriousness, severity, and relatedness.

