### **7.7.1 Laboratory evaluations**

Routine clinical monitoring will follow laboratory results when measured as part of usual care which may include daily complete blood count (CBC), renal function (creatinine/eGFR), electrolytes, D-dimer, CRP, and measures of coagulation (PT/PTT/INR). In the fostamatinib trial a daily CBC and liver function tests will also be performed while in the hospital on study drug.

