**Table 1. Schedule of Events**

Event	Baseline & Randomization Day 0	Day 1 – Day 28 	Discharge	Day 60	Day 90
Visit Windows		Day 7 and 14 + 1 Day Day 21 + 2 Days Day 28 + 5 Days		+ 10 Days	+ 14 Days
Confirm eligibility	X				
Obtain informed consent	X				
Screen by reviewing medical history and EMR	X				
Pregnancy test 	X				
Randomization	X				
Concomitant medications	X 	X 			
Record results of SOC laboratory assessments	X 	X			
Study-specific blood draws 					
• CBC with diff and LFTs in fostamatinib arm	X 	X			
Study-specific biological specimen collection 					
• EDTA plasma	X 	X			
• Serum					
Respiratory failure free days, oxygen free days and hospital free days	X 	X	X 		
WHO Ordinal Scale	X	X		X	
Mortality	X	X	X	X	X
Sequential Organ Failure Assessment score	X				
Initiate treatment 	X				
Continue study medication treatment		X			
Adverse event monitoring	X	X 		X	
Record discharge disposition			X		

 Perform events daily through day 28 or discharge, whichever occurs first. Only perform if patient is hospitalized.

 Perform for all women of childbearing potential.

 Perform only if not completed for current admission.

 Perform prior to treatment administration

 Only in the fostamatinib arm if not performed as part of usual care – performed daily while on study drug as an inpatient. A repeat CBC, LFTs and BP check may be necessary depending on values at discharge as indicated in [Appendix D: Arm 3: Fostamatinib](#).

 Coordinate with clinical lab draws when possible- as delineated in [Appendix C: Minimum Biological Specimen collection](#)

 Collect at Day 1, 3, 7, 14, 21, and 28 post-randomization if patient is discharged before 28 days.

 Administration route and timing/frequency is treatment specific

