**PSESEs are exempt from adverse event reporting unless:**

1. the event is determined to be Serious and Definitely or Possibly Related to the study drug or study procedures;
2. the event is determined to be Unexpected and Definitely or Possibly Related to the study drug or study procedures; or

This approach is taken to avoid creating an overly cumbersome safety oversight environment by identifying expected clinical outcomes as safety events and obscuring real safety signals. Even as they are exempted from expedited reporting requirements, PSESEs will be reviewed regularly (unblinded, by treatment arm) by the DSMB to maintain the integrity of safety monitoring for the trial. PSESEs that meet none of the criteria above will not be recorded or reported as AEs.

PSESEs may occur during the initial hospitalization, lead to a re-admission, or occur in a later hospitalization during follow-up. The following are study-specific exempt serious events:

- Death (not Definitely or Possibly Related to the study drug or study procedures)
- Neurological Events:
  - Seizure

- Stroke
- Cardiovascular Events:
  - Hypotension as defined by low arterial blood pressure leading to either [1] initiation or increase in vasopressor therapy, [2] administration of a fluid bolus of 500 ml or more, or [3] modification of the dose or discontinuation of the study drug.
  - Atrial or ventricular arrhythmia
  - Cardiomyopathy
  - Cardiac arrest
  - Myocardial injury
  - Acute coronary syndrome
  - Hypertension as defined by elevated arterial blood pressure leading to either [1] initiation or increase in antihypertensive medications or [2] discontinuation of the study drug
- Respiratory events:
  - Hypoxemia requiring supplemental oxygen
  - Acute respiratory distress syndrome
  - Receipt of non-invasive or invasive mechanical ventilation
  - Receipt of extra-corporeal membrane oxygenation
- Gastrointestinal events:
  - Elevation in aspartate aminotransferase or alanine aminotransferase
  - Acute pancreatitis
- Renal events:
  - Acute kidney injury
  - Receipt of new renal replacement therapy
- Endocrine events:
  - Symptomatic hypoglycemia
- Hematologic or coagulation events:
  - Neutropenia, lymphopenia, anemia, or thrombocytopenia
  - Venous thromboembolism
- Dermatologic events:
  - Severe dermatologic reaction (e.g., Steven's Johnson Syndrome)

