2.2 Study Arms and Pooled Placebo

The ACTIV 4 Host Tissue platform consists of multiple study arms that represent distinct drug therapies. During the randomization process, each participant is assigned a study arm and either the active drug or a matching placebo. The statistical analyses described herein will be implemented separately for each study arm. However, placebo participants will be pooled across arms. For each study arm, the placebo comparator group will consist of all placebo participants that were *eligible* for that study arm at the time of randomization. A participant is considered eligible for a study arm if assignment to that arm was a possible outcome of randomization. Participants that decline to participate in any one or more study arms prior to

randomization will be treated as ineligible for those arms. The randomization process is designed to ensure balance in each active drug group versus the corresponding placebo comparator group.

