2.3 Randomization

Participants are randomized individually at enrollment using a central electronic system. The permuted block method, with stratification by study site and study arm eligibility is used to generate treatment assignments. An eligibility stratum is the collection of study arms for which a participant is eligible. Stratification by site ensures balance across the active and pooled placebo comparator groups at regular enrollment intervals at each site, thus mitigating the impact of site heterogeneity on assessments of treatment effect. Each block contains a multiple of $m(m+1)$ assignments, where m is the number of study arms in the corresponding eligibility stratum. Within each block there are an equal number of allocations across study arms and, for each study arm, there are m active and 1 placebo assignments. For example, in the TXA127 and TRV027 eligibility stratum, each block consists of the following allocations, or multiples thereof:

Study Arm	Placebo/Active
TXA127	Active
TXA127	Active
TXA127	Placebo
TRV027	Active
TRV027	Active
TRV027	Placebo

Thus, within each block, assignments are balanced across study arms, and the active assignments are balanced with the pooled placebo assignments. The block size multiple is either 1 or 2, selected uniformly at random for each block.

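### Lab-detected safety events on fostamatinib are compared only with placebo pooled over arms, although study-mandated CBC/LFT draws apply only in the fostamatinib arm; a matched-placebo comparison should be reported beside the pooled one

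*SAP*

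**What the plan says.** **Comparator.** SAP section 7 runs the final safety analysis by "comparing each active drug group with the corresponding pooled placebo comparator group". SAP 2.2 defines the comparator as "all placebo participants that were *eligible* for that study arm at the time of randomization", whichever arm they were assigned to. Protocol 6.7 disregards placebo route and frequency: "all placebo participants will be pooled together as a single group". Within a randomization block (SAP 2.3), "for each study arm, there are m active and 1 placebo assignments", where m is the number of arms for which the participant is eligible.

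**Laboratory schedule.** Protocol 7.7.1: "In the fostamatinib trial a daily CBC and liver function tests will also be performed while in the hospital on study drug". Footnote 5 to Table 1 limits the study-specific draw: "Only in the fostamatinib arm if not performed as part of usual care". For all arms, 7.7.1 and item 3 of 7.7.6 describe CBC and liver tests as part of routine care, recorded when done.

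**Outcomes.** The PSESE list in Protocol 13.2 includes "Elevation in aspartate aminotransferase or alanine aminotransferase", with no threshold stated there, and neutropenia, lymphopenia, anemia and thrombocytopenia. SAP 3.3 analyses a row called *Other PSESE* as occurrence of at least one event by day 7 and by day 28. The logistic model (SAP 7.1.2) adjusts for age group, sex and baseline WHO score only.

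**Matched placebo.** Protocol 22.7 applies the fostamatinib rules to active and placebo participants in that arm alike, so a like-for-like control exists. No safety analysis uses it.

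**The concern.** Pooling placebo suits oxygen-free days, which are ascertained the same way in every arm. It is less safe for events that exist in the data only if a blood sample was taken. All fostamatinib recipients fall under the mandated draw; in the comparator, only fostamatinib-matched placebo participants do. If usual care samples less often than the mandate, some events in other-arm placebo participants go unseen, and the odds ratio for fostamatinib exceeds 1 even when the drug does nothing. The model has no term for assigned arm or testing schedule to absorb this.

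Liver enzyme elevation and neutropenia are among fostamatinib's labelled warnings (Protocol 22.5), so a modest spurious excess could easily be read as confirmation of a known risk.

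**Working it through.** **Step 1: share of other-arm placebo.** SAP 2.3 gives m(m+1) assignments per block (or a multiple), with m active and 1 placebo per arm. For m = 2 that is 6 assignments, 2 active and 1 placebo per arm, and 2 pooled placebos, which reproduces the SAP's TXA127/TRV027 example. Each arm's m actives therefore face m pooled placebos, of which one is matched. The other-arm share is 1 − 1/m:

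- m = 1: 0%
- m = 2: 50%
- m = 3: 67%

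The documents do not give the mix of m among fostamatinib participants.

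**Step 2: spurious odds ratio under no drug effect.** The documents give neither the event rate p nor the detection d in other arms relative to the fostamatinib schedule. I assume p = 10% or 20% and d = 90% or 70%.

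Observed placebo rate = p × [1/m + (1 − 1/m) × d]. Spurious OR = odds(p) / odds(observed placebo rate).

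| m | p | d | Observed placebo rate | Spurious OR |
|---|---|---|---|---|
| 2 | 10% | 90% | 9.5% | 1.06 |
| 2 | 20% | 90% | 19.0% | 1.07 |
| 3 | 10% | 90% | 9.3% | 1.08 |
| 3 | 20% | 90% | 18.7% | 1.09 |
| 2 | 10% | 70% | 8.5% | 1.20 |
| 2 | 20% | 70% | 17.0% | 1.22 |
| 3 | 10% | 70% | 8.0% | 1.28 |
| 3 | 20% | 70% | 16.0% | 1.31 |

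Worked line (m = 3, p = 20%, d = 70%): 0.20 × (1/3 + 2/3 × 0.7) = 0.16; (0.20/0.80) / (0.16/0.84) = 0.2500/0.1905 = 1.31.

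**Step 3: precision of a matched-only comparison.** With 300 active participants and 300/m matched placebos, the variance of the log OR is proportional to 1/300 + m/300, against 2/300 for the pool. The SE ratio is √((1 + m)/2): 1.00 for m = 1, 1.22 for m = 2, 1.41 for m = 3. These are the extremes in which every fostamatinib participant was randomized with that m.

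**Step 4: when would matching alone be better?** On mean squared error, dropping other-arm placebo pays only if (log spurious OR)² exceeds the added variance, [1/p + 1/(1 − p)] × (m − 1)/300.

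- p = 10%: 11.11 × 1/300 = 0.0370, so break-even OR = exp(√0.0370) = 1.21 (m = 2). 11.11 × 2/300 = 0.0741 gives 1.31 (m = 3).
- p = 20%: 6.25 × 1/300 = 0.0208 gives 1.16 (m = 2). 6.25 × 2/300 = 0.0417 gives 1.23 (m = 3).

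At d = 90% the spurious OR is below break-even throughout. At d = 70% it is below at p = 10% (1.20 against 1.21; 1.28 against 1.31) and above at p = 20% (1.22 against 1.16; 1.31 against 1.23). Neither comparator dominates, which argues for reporting both.

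**The case against.** The strongest reply is that the detection gap may hardly exist. Protocol 7.7.6 lists daily CBC and LFTs as routine care for all arms, and the fostamatinib draw only tops up what usual care omits. Nothing in the documents supports a relative detection as low as 70%. That stands, and it is why the 90% row deserves at least equal weight. It does not close the point: routine sampling in other arms is not required, and no planned analysis would show whether it happened.

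Other parts of the reply also stand:

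- Safety is not formally tested (SAP 5), and isolated laboratory abnormalities without signs or symptoms are not collected as adverse events (Protocol 13). The PSESE list still contains the laboratory items.
- *Other PSESE* also covers death, ARDS, ventilation and much else. If it is analysed as one composite, the laboratory items are diluted and the odds ratios above do not describe it.
- With only fostamatinib open, the bias is zero. This protocol version carries only the fostamatinib appendix, so that may hold for part of enrolment.

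A reader might infer more than the documents support:

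- *That post-discharge visits add much to the imbalance.* The BP, LFT and CBC rechecks in Protocol 22.7 mostly follow values already abnormal or rising at discharge, so they add few first events to an outcome of one or more events.
- *That hypotension is biased against fostamatinib.* One limb of its definition is modification or stopping of study drug, and Protocol 7.7.6 records infusions stopped for hypotension. Placebo infusions in other arms could raise the comparator rate, so the direction is unknown.
- *That diarrhea is affected.* It is neither laboratory-detected nor on the PSESE list.
- *That the DSMB necessarily sees the biased contrast.* The SAP 7 sentence governs the final analysis. SAP 7.2 promises frequencies without naming a comparator, and Protocol 13.2 has PSESEs reviewed unblinded by treatment arm.

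**Conclusion.** The point holds for AST/ALT elevation and the hematologic PSESEs, as a possible detection bias against fostamatinib whose size the documents do not settle. Under the stated assumptions it ranges from negligible (no other arm open, or detection close to equal) through an odds ratio of 1.06 to 1.09 at 90% relative detection to 1.20 to 1.31 at 70%. The event rates and detection fractions are mine, and the other-arm shares assume that all fostamatinib participants had the same number of open arms. The absence of mandated draws elsewhere rests on Protocol 7.7.1 and Table 1, because the other arms' appendices are not in this version.

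It would be wrong to conclude that the pooled comparison is invalid, that fostamatinib's labelled risks will be exaggerated as a class, or that matched placebo must replace the pool. The defect is narrower: a like-for-like comparison is available and has not been prespecified for the events that need it.

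**What to change.** In SAP 3.3 and 7, report AST/ALT elevation and the hematologic PSESEs (neutropenia, lymphopenia, anemia, thrombocytopenia) separately from the other PSESEs. For these events, add a prespecified final-analysis comparison of fostamatinib with fostamatinib-matched placebo, placed beside the pooled-placebo comparison, and state that a pooled signal will be interpreted in its light. Because active and matched placebo are allocated m to 1, and m varies by eligibility group, the matched model should also be stratified by or adjusted for eligibility group.

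The cost is SAP wording and one extra table. The matched estimate is less precise, with the SE of the log OR up to about 22% higher with two arms open and 41% with three, and no loss where only fostamatinib was open. The pooled estimate is retained, so no information is given up. Under no drug effect the matched comparison has an expected odds ratio of about 1, since both groups follow the same testing schedule.

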7.1 Statistical Methods for Secondary, Exploratory, and Safety Analyses

The methods described below will be applied uniformly to the examine the effect of each active drug versus the placebo comparator on the secondary, exploratory, and safety outcomes, as appropriate.

7.1.1 Proportional Odds Logistic Regression (POLR)

Ordinal secondary, exploratory, and safety outcomes will be analyzed using a method similar to that described above for the analysis of the primary outcome, using proportional odds logistic regression (POLR), and adjusting for participant age group, sex, and WHO COVID ordinal severity at baseline. The effect of the active drug versus placebo will be presented using an odds ratio which quantifies the treatment effect on the odds of greater values of the ordinal outcome. The odds ratio will be presented with 95% credible interval. A flat prior distribution will be used for all model parameters. The posterior distribution for the log odds ratio will be approximated using the Laplace method. All statistical inferences about the odds ratio will be made using this method. The proportional odds assumption means that the odds-ratio has the same interpretation for all dichotomizations (that preserve ordering) of the ordinal outcome. The repeated dichotomization method, as described for the analysis of the primary outcome, will be used to assess for severe violations of the proportional odds assumptions. Missing or partially observed outcomes will be handled using the likelihood method as described for the primary analysis (see *Loss to Follow-up, Censoring, and Intercurrent Events*).

7.1.2 Logistic Regression (LogR)

Binary secondary, exploratory, and safety outcomes will be analyzed using logistic regression (LogR), and adjusting for participant age group, sex, and WHO COVID ordinal severity at baseline. The effect of the active drug versus placebo will be presented using an odds ratio which quantifies the treatment effect on the odds of outcome occurrence. The odds ratio will be presented with 95% credible interval. In addition, to facilitate clinical interpretability and meaningfulness, the difference in proportions corresponding to the most common (modal) values of the adjustment variables will be presented with 95% credible interval. A flat prior distribution will be used for all model parameters. The posterior distribution for the log odds ratio will be approximated using the Laplace method. All statistical inferences about the odds ratio and other posterior quantities will be made using this method. Missing outcomes will be handled using the likelihood method as described for the primary analysis (see *Loss to Follow-up, Censoring, and Intercurrent Events*).

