3.3 Safety Outcomes

Safety outcomes include the following events, assessed daily during hospitalization or intermittently following hospital discharge. For each event, we will analyze two composite binary outcomes: 1) the occurrence of one or more such events by the end of study day 7 and 2) the occurrence of one or more such events by the end of study day 28.

Description	Type	Analysis Method
Hypotension	Binary	LogR
Allergic reaction, rash, or angioedema	Binary	LogR
Incident renal replacement therapy	Binary	LogR
Other PSESE	Binary	LogR

LogR – Logistic Regression

Hypotension is defined by low arterial blood pressure leading to either [1] initiation or increase in vasopressor therapy, [2] administration of a fluid bolus of 500 ml or more, or [3] modification of the dose or discontinuation of the study drug.

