patient on treatment A,¹³ the *probability index* or *concordance probability*. In addition, under the null hypothesis, the PO assumption is always satisfied. Thus, statistical testing based on the odds ratio, as estimated using the PO model, has the specified type-I error rate and provides a reasonable global assessment of treatment effectiveness, regardless of violations of the proportional odds assumption. However, derived quantities such as the difference in means may be more sensitive to violations of the PO assumption. Deviations from proportional odds will be examined by separately estimating the odds ratio for each possible dichotomization (that preserves ordering) of the primary outcome (e.g., alive versus dead at day 28, alive and oxygen free for at least 10 days at day 28 versus alive and oxygen free for fewer than 10 days or dead at day 28, etc.), in a planned sensitivity analysis. These analyses will be implemented using the logistic regression method described below (see *Logistic Regression (LogR)*). No hypothesis testing will be implemented regarding the PO assumption. This sensitivity analysis serves the following two purposes: 1) to assess for evidence of violation of the proportional odds assumption and 2) to estimate the differential treatment effects (with 95% credible interval) when the proportional odds assumption is relaxed. The latter provides the information needed to interpret the treatment effects should there be evidence of violation of the proportional odds assumption. In addition, as a key secondary outcome, we will quantify the effect of treatment on 28-day mortality, which directly addresses the possibility that treatment affects 28-day mortality differently than cumulative oxygen use within the first 28 days. This analysis enables us to detect non-proportional effects of the treatment on the two major components of the primary outcome, mortality, and oxygen-free days.

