6.6 Sample Size and Decision Thresholds

The maximum number of participants to be enrolled in sub studies under the Master Protocol is 600 participants per trial, resulting in approximately 300 patients per active treatment arm, and 300 patients in the matching placebo arm. The placebo arm will be shared across all active treatment arms. We expect placebo participants to continue to accrue for as long as there are additional treatments to test and cases to enroll.

Type-I error and power regarding the analysis of the primary outcome was assessed based on the pooled (across all active and placebo arms) distribution of the primary outcome among the first 100 participants to complete follow-up and monitoring. The efficacy threshold was identified using statistical simulation under the null hypothesis to ensure the study operating characteristics achieve design specifications. Pooled and blinded summaries of oxygen-free days at day 28 were used to approximate the distribution of the oxygen free days in the placebo group. Based on these data, the anticipated frequency distribution, mean, and median of oxygen-free days (OFDs) for the placebo group, and for the treatment group under hypothetical effect sizes computed using the PO model are displayed in the table below.

OFDs / Odds Ratio	Placebo	Inferiority		Superiority						
		0.67	0.80	1.40	1.45	1.50	1.55	1.60	1.65	1.70
Mean	8.8	6.6	7.5	10.8	11.1	11.3	11.5	11.7	11.9	12.0
Median	0	0	0	6.5	7.5	9.0	10.0	10.5	12.5	14.5
P(OFDs \geq 22)	0.19	0.14	0.16	0.25	0.26	0.26	0.27	0.28	0.29	0.29
Proportion:										
-1 (death)	0.235	0.316	0.279	0.181	0.176	0.171	0.166	0.162	0.158	0.154
0	0.296	0.314	0.309	0.268	0.264	0.261	0.257	0.254	0.251	0.247
1	0.006	0.006	0.006	0.006	0.006	0.006	0.006	0.006	0.006	0.006
---	---	---	---	---	---	---	---	---	---	---
27	0.050	0.034	0.041	0.069	0.072	0.074	0.076	0.078	0.081	0.083
28	0.000	0.000	0.000	0.000	0.000	0.000	0.000	0.000	0.000	0.000

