11.3 Model Fitting and Computation

The cumulative logit model is implemented in the R code file “`clm_model.R`”. Readers should examine the `clm_fit` function first, which is the entry point for model fitting, and then examine other functions as they are called by `clm_fit`. The function `clm_fit` takes as arguments the matrix of coded covariates x , and a matrix of coded outcomes y . Each matrix has one row per record (i.e., study participant). The covariate matrix has one column per coded covariate (e.g., age group has three levels and thus requires two columns to distinguish the levels), and the outcome matrix has one column per value that the outcome might take. The cells of the outcome matrix y contain the values y_{ij} as defined above (see “Model Formulation”).

In practice, when one or more levels of an ordinal outcome are not observed in the analysis data set, some of the model intercepts are not estimable (i.e., there is no unique set of model intercepts that maximizes the likelihood/posterior density function). To overcome this, each outcome level is characterized as “estimable” if there is at least one record in the analysis data set where that level is observed and no other level was possible (i.e., ignoring partially observed outcomes), and “not estimable” otherwise. Levels of the outcome that are not estimable are collapsed with the nearest adjacent estimable level to form a new level, e.g., levels 3, 4, and 5 may be collapsed to form level “3|5”. When levels are collapsed, if any collapsed level was possible as part of a partially observed outcome, then the collapsed level is considered possible as well. This functionality is implemented by the function `clmCollapse`, which is called by `clm_fit` prior to any model fitting.

The estimate of θ is found by maximizing the log of the posterior density function (i.e., a maximum *a posteriori* estimate, or MAP for short) defined in expression (5). Note that the normalizing constant in expression (5) is not needed to identify the MAP estimate, nor is it necessary to form a Laplace approximation to the posterior density. The estimate of θ is found using an iterative optimization algorithm, and the associated observed Fisher information is estimated using a finite difference method. These calculations are implemented using the R function `optim`, which uses the quasi-Newton “BFGS” method (Byrd, Lu, Nocedal, and Zhu,

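### SAP 7.1.2 has no fallback for a binary safety outcome with no events in one arm, where the planned odds ratio and credible interval cannot be estimated

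*SAP*

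**What the plan says.** SAP 3.3 lists four binary safety outcomes for logistic regression, each counted by day 7 and by day 28. One is "Allergic reaction, rash, or angioedema"; the others are hypotension, incident renal replacement therapy and other PSESE.

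SAP 7.1.2 sets the method: "A flat prior distribution will be used for all model parameters", and "The posterior distribution for the log odds ratio will be approximated using the Laplace method". The model adjusts for age group, sex and baseline WHO score. The outputs are an odds ratio and a difference in proportions at the modal covariate values, each with a 95% credible interval. Nothing is said about sparse outcomes.

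SAP 11.3 deals with non-estimability for the cumulative logit model: "Levels of the outcome that are not estimable are collapsed with the nearest adjacent estimable level". It describes an R BFGS optimizer and adds that "the associated observed Fisher information is estimated using a finite difference method".

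SAP 6.5 also uses logistic regression to check proportional odds, by "separately estimating the odds ratio for each possible dichotomization (that preserves ordering) of the primary outcome".

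**The concern.** A flat prior with a normal approximation at the mode needs a mode. When one arm has no events, the likelihood keeps rising as the log odds ratio grows, so there is no maximum and the flat-prior posterior cannot be normalised. Software still returns a number, but that number reflects starting values and the convergence tolerance, not the data.

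Allergic reaction or angioedema by day 7 could plausibly be this rare. What is at stake is one planned summary for such an event, the odds ratio and its interval, which would carry no information in the case where a safety reader most wants it.

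**Working it through.** The documents give no safety event rate and no worked safety result, so there is no plan figure to reproduce.

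**Inputs.** Sample size: "approximately 300 patients per active treatment arm, and 300 patients in the matching placebo arm" (SAP 6.6). Flat prior and Laplace posterior (SAP 7.1.2). BFGS optimizer (SAP 11.3; assumed to carry over to binary outcomes). Illustration: 6 of 300 active versus 0 of 300 placebo, without covariates.

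**1. No maximum exists.** Let a be the placebo log odds, b the log odds ratio, p0 = expit(a) and p1 = expit(a + b). The log likelihood is 6 log p1 + 294 log(1 − p1) + 300 log(1 − p0). Maximising over a at fixed b gives:

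| b | 4 | 6 | 8 | 10 | 14 | 20 |
|---|---|---|---|---|---|---|
| log likelihood | −29.523 | −29.427 | −29.414 | −29.4120 | −29.4117 | −29.4117 |

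The ceiling is 6 log 0.02 + 294 log 0.98 = −23.472 − 5.940 = −29.412. It is approached but never reached at a finite b.

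**2. What the fit returns.** The variance of b is 1/[300 p0(1 − p0)] + 1/[300 p1(1 − p1)]. BFGS started at the pooled log odds, log(6/594) = −4.595, stops at a = −17.67 and b = 13.8. There p0 is about 2.1 × 10⁻⁸, so the first term is about 158,000, the second is 0.17, and the standard error is about 398. The 95% interval for b is 13.8 ± 1.96 × 398, or about −766 to 794. Started at zero, the same routine stops at b = 17.4 with a standard error of about 2,390. A separate BFGS implementation gave b = 9.3 with standard error 46 for 5 versus 0, and standard GLM iteration gave 17.5 with 2,783 for the same table. The data alone do not determine the answer.

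For comparison, Fisher's exact one-sided p for 6 versus 0 is 0.015. One placebo event restores the method: 10 versus 1 gives an odds ratio of 10.3 (1.3 to 81).

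**3. The collapsing rule does not help.** It acts on outcome levels with no fully observed record in the whole analysis set. With 6 versus 0, both levels (event and no event) are observed, so nothing is collapsed.

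**4. How often it could happen.** With the same true rate r in both arms and q = (1 − r)³⁰⁰, the chance that exactly one arm is empty is 2q(1 − q). The rates are assumptions.

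| r | q | exactly one arm empty |
|---|---|---|
| 0.2% | 0.548 | 49.5% |
| 0.5% | 0.222 | 34.6% |
| 1% | 0.049 | 9.3% |
| 2% | 0.0023 | 0.5% |

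**5. What the other planned output gives.** The unadjusted risk difference for 6 versus 0 is 0.020, with delta-method standard error √(0.02 × 0.98/300) = 0.0081 (the placebo term vanishes). That is 2.0 points (0.4 to 3.6). The planned version is taken at modal covariates. Under an assumed covariate mix it stayed finite, at about 2.1 points (−0.9 to 5.3).

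**6. What a penalised fit gives.** In the unadjusted table, Firth's penalty equals adding 0.5 to each cell: (6.5 × 300.5)/(294.5 × 0.5) = 13.3. The Wald standard error is √(1/6.5 + 1/294.5 + 1/0.5 + 1/300.5) = 1.47, giving 0.74 to 237. Profiling the penalised likelihood (a drop of 3.84/2 from its maximum) gives 1.56 to about 1,730, which agrees better with Fisher's test. So the interval method needs specifying too. A score interval for the risk difference is 0.7 to 4.3 points.

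**The case against.** The strongest reply is that nobody would be misled. Protocol 8.8 and SAP 7.2 report frequencies, Protocol 13.2 has the DSMB review PSESEs unblinded by arm, SAP 5 allows descriptive p-values for DSMB safety requests, and the risk difference does not diverge. A reader would see 6 versus 0. This stands and limits the point. It does not repair the odds ratio, which SAP 7.1.2 and Protocol 8.8 both promise with an interval. The risk difference is also only a partial substitute. Its adjusted interval included zero in the check above, and the delta method is documented for the primary supplementary estimands but only assumed here.

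Four stronger readings are tempting, and the documents do not support them.

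- A reader might infer that rare signals would be reported as a near coin-flip probability of harm. Posterior probabilities are planned for the primary outcome and, in the efficacy direction, the key secondary outcomes. SAP 7.1.2 would allow one for safety but does not plan it.
- A reader might infer that an empty covariate cell also spoils the treatment effect. In a simulated set with 15 versus 8 events and none in the youngest age group, the age coefficient diverged. The treatment log odds ratio (0.656, standard error 0.450) matched the fit without that group to about five decimals.
- A reader might take the 0.000 for 28 oxygen-free days in the SAP 6.6 table as a hidden signal. It is a rounded planning figure. If nobody reaches 28, both arms are empty and there is no contrast to miss.
- A reader might compute the chance of an empty arm as 1 − (1 − q)², which gives 40% at 0.5% and 80% at 0.2%. That counts zero events in both arms, where nothing can be missed.

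**Conclusion.** The point holds in a limited form. For a binary safety outcome with events in only one arm, the method in SAP 7.1.2 yields an odds ratio and credible interval that are artefacts of the optimizer, and neither document names an alternative. This is worth correcting before analysis because the stated method gives an unusable planned result, not merely because detail is missing.

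Its reach is narrow. It needs true rates below roughly 1 to 2% per arm, so it matters for outcomes such as allergic reaction or angioedema and is implausible for the broad other-PSESE composite. No stopping rule, test or threshold uses the safety odds ratios. The primary analysis, type I error, power and key secondary tests are unaffected.

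The non-existence of the estimate follows from the likelihood and rests on no assumption. The size of the returned numbers rests on the assumed optimizer, and the frequencies on assumed event rates.

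**What to change.** In SAP 7.1.2, add that when a binary safety outcome has no events in one arm, or fewer than a pre-specified number, three things will be reported:

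- the odds ratio from a Firth (Jeffreys) penalised logistic fit, with profile-penalised-likelihood intervals;
- the event counts per arm;
- an exact or score interval for the unadjusted risk difference.

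In SAP 6.5, use the same penalised fit for any oxygen-free-day cut with an empty cell in one arm, and skip cuts with no events in either arm. SAP 7.1.2 should also name the optimizer and the interval method for the difference in proportions, since both had to be assumed here.

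The cost is a few sentences and a standard function. The downside is slight shrinkage of the odds ratio in sparse outcomes. The primary analysis and the key secondary tests stay as they are.
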